4.1.3 Exclusion Criteria

Any of the following would exclude the subject from participation in the study:

Criteria to be Assessed at Screening Visit 1 and Visit 2:

If any criterion cannot be fully assessed at screening Visit 1 and Visit 2 (eg, laboratory results not yet available), the criterion must be fully assessed prior to randomization.

- Subjects with a recent history of or who have a positive test for infective hepatitis, HIV, or unexplained jaundice, or subjects who have been treated for hepatitis B, hepatitis C, or HIV. For the hepatitis B testing (hepatitis B surface antigen [HbsAg], hepatitis B surface antibody [anti-HBs], and hepatitis B core antibody [anti-HBc]), any of the following would exclude the subject from the study:
 - (a) Subjects positive for HbsAg.
 - (b) Subjects positive for anti-HBc.

Subjects with a history of hepatitis B vaccination without a history of hepatitis B are permitted.

- 2 Evidence of active or latent tuberculosis (TB):
 - (a) Positive diagnostic TB test during screening Visit 1 defined as a positive interferon gamma release assay [IGRA] test).

- (b) Subjects with an indeterminate IGRA should undergo a repeat test and if still indeterminate may be enrolled only after being treated for TB and having a subsequent negative test.
- (c) Subjects with a positive IGRA but no clinical history or suspicion of TB and no significant risk factors for TB may undergo a retest and be enrolled if that result is negative.
- 3 N-terminal prohormone of B-type natriuretic peptide (NT-proBNP) level greater than the upper limit of the laboratory reference range at screening Visit 1; if the result is greater than the upper limit but this is clinically unexpected, the test may be repeated once.
- 4 A left ventricular ejection fraction < 45% measured by echocardiogram during screening, between the time of signing informed consent and prior to randomization.
- 5 A family history of heart failure defined as either of the following:
 - (a) ≥ 2 first degree relatives with clinically significant heart failure, or
 - (b) ≥ 1 first degree relative with heart failure known to be heritable (eg, hypertrophic cardiomyopathy), unless inheritance is excluded by genetic testing.

Criteria to be Assessed at Screening Visit 1, Visit 2, and Visit 3 (Day 1) Prior to Randomization:

- 6 Concurrent enrollment in another clinical study involving an investigational product.

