Lesional and non-lesional skin swabs for Staphylococcus aureus i	X								X
Skin punch biopsies ^k	X								X
Adhesive skin tape patches	X								X
Application of stable dose of topical emollient (moisturizer)			Τν	Twice daily throughout treatment period	oughout treat	ment period			
	-					_			

Table 7 Schedule of Treatment Period Study Procedures

	Visit 10	H	
	Visit 9 Visit 10	-	
	Visit 8		
	Visit 7	H	
Treatment Period	Visit 6	OO O	
Treat	Visit 5		
	Visit 4b ^b		
	Visit 4a ^b TC		
	Visit 3 a		
eriod	mber		
Study Period	Visit Number		
S	>		

Outcome Test; sST2 = soluble ST2; TC = telephone contact; TEAE = treatment-emergent adverse event; TESAE = treatment-emergent serious adverse event. proBNP = N-terminal prohormone of B-type natriuretic peptide; PBMC = peripheral blood mononuclear cell; PGI-S = Patient Global Impression of Severity; DLQI = Dermatology Life Quality Index; EASI = Eczema Area and Severity Index; ECG = electrocardiogram; eDiary = electronic diary; EDN = eosinophil POEM = Patient-Oriented Eczema Measure; PK = pharmacokinetic(s); SC = subcutaneous; SCORAD = SCORing Atopic Dermatitis; SNOT = Sino-nasal ACQ = Asthma Control Questionnaire; AD = atopic dermatitis; ADA = anti-drug antibody(ies); BSA = body surface area; CPT = Cell Preparation Tubes; derived neurotoxin; Ig = immunoglobulin; IGA = Investigator's Global Assessment; IL = interleukin; NRS = Numerical Rating Scale; NT-

- Specifications for moisturizer use prior to visits when SCORAD will be assessed are described in Section 4.3.1.3.
- Subjects must be assessed on IGA, EASI, and SCORAD rating scales prior to randomization to ensure the subjects still qualify for the study. Visit 4a only applies to the first 72 subjects randomized, subsequent subjects will attend Visit 4b instead, as described in Section 3.1.1.
 - SNOT-22 and ACQ-6 will be administered to a subset of subjects only as described in Sections 4.3.1.11 and 4.3.1.12, respectively.
 - At the visits specified, the physical examination will include an alopecia areata assessment as described in Section 4.3.2.2
 - Detailed procedures including the frequency and timing of ECGs by visit are described in Section 4.3.2.4.
 - Detailed procedures and the timing of vital signs are described in Section 4.3.2.3
- Echocardiogram may be performed at any time at or between Visit 9 (Week 12) and Visit 10 (Week 16) inclusive.

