5.4.5 Recording of Injection Site Reactions

For AESIs of injection site reactions, the sign or symptom, and diameter of area will be recorded.

5.4.6 Recording of Cardiac Events (Including Angina or Myocardial Infarction, Congestive Heart Failure, Symptomatic Atherosclerotic Vascular Disease, or Pulmonale or Arrhythmia)

For subjects with AESIs of cardiac events suggestive of new onset and/or progression of heart failure, left ventricular ejection fraction measured by echocardiogram and NT-proBNP will be recorded.

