3 STATISTICAL METHODS

3.1 General Considerations

In general, unless specified otherwise, baseline is defined as the last non-missing assessment prior to dosing. If the baseline is missing following the above definition, baseline evaluations will not be imputed and will be considered as missing. All safety analyses will be performed on the As-treated population. All PK analyses will be conducted using the PK-population. Immunogenicity evaluation will be based on the As-treated population. All other analyses will be performed on the ITT population unless stated otherwise. All data will be provided in data listings sorted by treatment group and subject number. The placebo CCI groups will be pooled for planned analyses, except where stated otherwise. All tabular summaries will be presented by treatment group. Categorical data will be summarized by the number and percentage of subjects in each category. Continuous variables will be summarized by descriptive statistics including number of subjects, mean, standard deviation (SD), median, minimum, and maximum. All statistical tests will be two-sided at an alpha = 0.1 significance level unless stated otherwise.

Day 1 is the first dosing date. Prior to Day 1, study days will be calculated as (sample collection date – Day 1). After Day 1, study days will be calculated as (sample collection date – Day 1 + 1).

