3.1.2 Visit Windows

Visit windows will be used for all scheduled assessments to allow for by-visit analyses, since not all assessments are performed on the scheduled day. The analysis visit windows will be calculated by bisecting the scheduled visit days. The lower limit of each window will be the mean of the two adjacent planned study days, rounded up to the nearest integer. The upper

limit of each window will be the mean of the two adjacent planned study days, rounded down to the nearest integer.

The visit result will be missing if no assessment was reported within the specified visit window around the scheduled date. If multiple readings are recorded within a single visit window, then rules will be applied, as follows:

- If there are 2 or more observations within the same visit window, the non-missing observation closest to the scheduled visit will be used in the analysis.
- If 2 observations are equidistant from the scheduled visit, the non-missing observation with the earlier collection date or time will be used in the analysis.
- If two observations are collected on the same date, the non-missing observation with the earlier collection time will be used in the analysis.
- Additional rules for cases not covered by the 2 rules above will be documented in the Analysis Conventions Document.

For EASI, IGA and SCORAD, adjusted protocol-defined visit windows will be used as defined in

[Table 1.](#)

Table 1 Adjusted Protocol-defined Visit Windows for EASI, IGA, and SCORAD

Visit Number	Name/Week Number	Scheduled Study Day in the Protocol	Visit Windows
1	Screening ^a	-28 to -12	Study Day \leq -12
2	TCS/TCI Wash Out ^a	-11 to -8	-11 \leq Study Day \leq -8
3	Week 0 (Day 1) ^a	1	-7 \leq Study Day \leq 1
5	Week 1	8	2 \leq Study Day \leq 11
6	Week 2	15	12 \leq Study Day \leq 22
7	Week 4	29	23 \leq Study Day \leq 43
8	Week 8	57	44 \leq Study Day \leq 71
9	Week 12	85	72 \leq Study Day \leq 99
10	Week 16	113	100 \leq Study Day \leq 127
11	Week 20	141	128 \leq Study Day \leq 155
12	Week 24	169	Study Day \geq 156

^a The Screening and Week 0 (Day 1) visit windows are applicable only when the visit is present for descriptive statistics in the summary tables for EASI, IGA, and SCORAD. For analyses, baseline is defined as the last assessment value prior to dosing unless stated otherwise.

For the patient-reported questionnaires collected by electronic PRO, the data will be summarized based on the visit windows provided (Table 2).

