3.6.6 ECGs and Left Ventricular Ejection Fraction

An electrocardiogram (ECG) will be performed to confirm that MEDI3506 does not affect cardiac electrophysiological intervals.

The computerized triplicate 12-lead ECG results and QT intervals (msec) will be summarized descriptively by treatment group and visit for each of the ECG variables collected (heart rate, RR interval, QRS interval, PR interval, QT interval (using both Fridericia's correction: $QTcF[\text{msec}] = QT[\text{msec}]/(RR[\text{sec}]^{1/3})$ and Bazett's correction: $QTcB[\text{msec}] =$

$QT[msec]/(RR[sec]^{1/2})$). For the triplicate 12-lead ECG, an average of 3 reads will be used. Changes from baseline will be summarized by treatment group and visit into 3 categories: increase ≤ 30 msec, $30 \text{ msec} < \text{increase} \leq 60$ msec, and increase > 60 msec. Shift tables for QTc intervals ($QTc \leq 450$ msec, $450 < QTc \leq 480$ msec, $480 \text{ msec} < QTc \leq 500$ msec, $QTc > 500$ msec) will be presented to compare the baseline ECG evaluation and the post-dose evaluations. In addition, descriptive summary of qualitative ECG results by visit will be provided.

Left ventricular ejection fraction, as measured by echocardiogram, will be summarized descriptively by treatment group and visit.

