3.6.7 Other safety tests

NT-proBNP results will be summarized descriptively by treatment group at each visit and change from baseline summarized for each post-baseline visit. The summary based on the number and percentage of participants above or below the normal range will be produced as well as shifts from baseline relative to the normal range. A boxplot showing the distribution of NT-proBNP by treatment arm and visit will be provided. NT-proBNP results will be provided in the by-subject listings as reported and values outside of the normal range will be flagged.

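### LVEF gets no change-from-baseline summary, and the SAP has no worst-value rule for for-cause echocardiogram and NT-proBNP results

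*SAP*

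**What the plan says.** **Collection.** Protocol 2.2 (Table 2) lists LVEF by echocardiogram among the secondary safety endpoints. Table 6 places an echo in screening, with the result needed before randomization. Table 7 enters one planned on-treatment echo, at Visit 9, with the footnote "Echocardiogram may be performed at any time at or between Visit 9 (Week 12) and Visit 10 (Week 16) inclusive". Tables 7 and 8 also call for NT-proBNP and echo as required when heart failure is suspected. For cardiac events that suggest new or progressing heart failure, Protocol 5.4.6 says that "left ventricular ejection fraction measured by echocardiogram and NT-proBNP will be recorded".

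**LVEF analysis.** SAP 3.6.6 gives one sentence: "Left ventricular ejection fraction, as measured by echocardiogram, will be summarized descriptively by treatment group and visit". Protocol 4.8.4.3 adds no detail. SAP 3.1 defines the summary of a continuous variable as "descriptive statistics including number of subjects, mean, standard deviation (SD), median, minimum, and maximum".

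**NT-proBNP analysis.** SAP 3.6.7 says "NT-proBNP results will be summarized descriptively by treatment group at each visit and change from baseline summarized for each post-baseline visit". It adds counts outside the normal range, shifts from baseline, a boxplot and a flagged listing.

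**Choice of value.** SAP 3.1.2 says "Visit windows will be used for all scheduled assessments to allow for by-visit analyses". When two or more values share a window, "the non-missing observation closest to the scheduled visit will be used in the analysis", and the earlier value wins a tie. Cases the rules do not cover go to an Analysis Conventions Document.

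**The concern.** Cardiac events are an adverse event of special interest, and Protocol 9.8 records that the echo and NT-proBNP measurements were added in response to a regulator's safety concerns. The question for LVEF is whether individual subjects lose function on treatment. Answering it needs each subject's own baseline, which the trial collects and the planned LVEF summary does not use.

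The second issue is which value is used. For-cause tests are done because something looks wrong, so they are more likely than routine ones to be abnormal. A rule that picks the value by closeness to a calendar day ignores that. For the tables where abnormality matters most, the NT-proBNP out-of-range and shift tables, the SAP does not say which values count.

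**Working it through.** **1. Which safety measures get a within-subject summary**

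| Measure | SAP section | Change from baseline | Shift or category table |
|---|---|---|---|
| Laboratory tests | 3.6.4 | yes | yes |
| Vital signs | 3.6.5 | yes | no |
| QTc | 3.6.6 | yes, in three categories | yes |
| NT-proBNP | 3.6.7 | yes | yes |
| LVEF | 3.6.6 | no | no |

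**2. What raw values cannot show**

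A single fall of size d moves the mean of an arm of n subjects by d/n. The planned arm sizes in Protocol 4.1.1 are 58, 18 and 18, with 58 for pooled placebo.

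- 15-point fall: 15/18 = 0.83 points; 15/58 = 0.26 points.
- 20-point fall: 20/18 = 1.11 points; 20/58 = 0.34 points.

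The other statistics do not fill the gap. Take ten constructed subjects with baseline LVEF 50, 52, ..., 68. In data set A every follow-up value equals its baseline. In data set B the same ten follow-up values are assigned in reverse order. Both follow-up sets have mean 59.0, SD 6.06, median 59, minimum 50 and maximum 68. A has no fall of 10 points or more. B has three: 64 to 54, 66 to 52 and 68 to 50. The planned LVEF table would be identical for both. In a change-from-baseline table the minimum would be 0 in A and −18 in B.

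**3. Effect of the closest-value rule on NT-proBNP**

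Check on the method: bisecting Days 8, 15, 29, 57, 85, 113, 141 and 169 reproduces the SAP Table 1 windows from Week 1 to Week 20, with each window starting the day after the previous one ends.

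NT-proBNP is scheduled at Visits 8, 9, 10 and 12 (Days 57, 85, 113 and 169). The midpoints are (57 + 85)/2 = 71, (85 + 113)/2 = 99 and (113 + 169)/2 = 141. The windows are therefore Days 2–71, 72–99, 100–141 and 142 onward.

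Example: a routine sample on Day 57 is normal and a for-cause sample on Day 68 is raised. Both fall in the first window, at distances 0 and 11 days. The Day 57 value is kept and Day 68 is absent from the by-visit summaries.

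Now count every possible for-cause day from Day 2 to Day 169, given that all scheduled samples are present. The size of the deviation from schedule is an assumption:

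| Scheduled samples taken | For-cause days that enter a by-visit summary |
|---|---|
| on the nominal day | 0 of 164 |
| 3 days early | 18 of 164 (11%) |
| 3 days late | 22 of 165 (13%) |
| 7 days early | 46 of 164 (28%) |
| 7 days late | 50 of 165 (30%) |

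**4. The same rule applied to the echo**

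Assume one post-baseline window with nominal Day 85 (Visit 9). If the planned echo is done on Day 85, none of the 167 other days can supply the value used. If it is done on Day 113, as the footnote allows, a for-cause echo on any of Days 57–112 (56 of 167, 34%) replaces the planned one. The value shown depends on timing alone.

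**5. How the SAP treats other safety data**

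SAP 3.7 uses each subject's maximum ADA titre for summaries across visits and gives early-discontinuation samples an assignment rule. SAP 3.6.2 counts subjects who cross liver thresholds. Neither LVEF nor NT-proBNP has a comparable worst-value rule.

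**The case against.** A reader might infer that for-cause results never reach the tables. The documents do not support that. A for-cause value that is alone in its window, or nearer the nominal day than the scheduled one, is used. SAP 3.1.2 sets windows for by-visit analyses, and SAP 3.6.7 does not tie the out-of-range counts and shifts to visits. Their value selection is unspecified; they are not shown to omit for-cause results. The Analysis Conventions Document, which is not available here, may settle it.

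There are also other routes. SAP 3.1 lists all data. Under Protocol 5.4.11, echo findings that need intervention or are judged medically significant are reported as adverse events. SAP 3.6.2 tabulates cardiac events of special interest by arm. All of this stands, but the event route depends on investigator judgement, and none of it gives a by-arm count of measured falls.

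The raw minimum is not useless either. Protocol 4.1.3 excludes "A left ventricular ejection fraction < 45% measured by echocardiogram during screening", so a post-baseline minimum of 42% would show that at least one subject had dropped below the entry threshold. It would not show how many had, nor any fall that stays above that minimum.

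A reader might also infer that the planned echo would split between a Week 12 and a Week 16 row. The documents point the other way: it has a single slot at Visit 9, and SAP Table 2 shows windows built on each assessment's own schedule (ACQ and SNOT-22 skip Weeks 2 and 20). Nor is precision the argument, since no LVEF group comparison is planned.

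**Conclusion.** The point holds in two parts. The LVEF part is firm and needs no assumption: a named safety endpoint, with a baseline for every subject, is the only measure in the table above without a change-from-baseline summary, and its planned statistics can be identical whether or not subjects fall.

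The for-cause part is firm as an omission. Its size is conditional. When a scheduled NT-proBNP is present in every window, between 0% (all on the nominal day) and about 30% (all 7 days late) of possible for-cause days would supply the by-visit value. These are shares of calendar days; they do not predict how many results would be affected. The echo figures rest on a single window with nominal Day 85.

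This concerns how cardiac safety data are summarized. No data are lost, and the efficacy conclusions are untouched. It should be corrected because the data are already collected and the change is small.

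**What to change.** **SAP 3.6.6.** Add LVEF change from baseline at the single planned post-baseline echo (Visit 9 to Visit 10). Tabulate by arm each subject's lowest post-baseline LVEF, with the number below 45%. That is the protocol's own entry threshold, used here only as a descriptive cut. The count will not pick up falls that stay above 45%; the minimum of the change from baseline covers the largest of those.

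**SAP 3.6.6 and 3.6.7.** State that the LVEF count and the NT-proBNP out-of-range and shift tables use the worst post-baseline value (lowest LVEF, highest NT-proBNP), including unscheduled and early-discontinuation results. Keep the closest-value rule of SAP 3.1.2 for by-visit summaries.

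**Cost.** A few sentences and table rows, with no new data. Worst-value tables count isolated outliers, so they should be shown beside the by-visit tables.

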3.6.7 Other safety tests

NT-proBNP results will be summarized descriptively by treatment group at each visit and change from baseline summarized for each post-baseline visit. The summary based on the number and percentage of participants above or below the normal range will be produced as well as shifts from baseline relative to the normal range. A boxplot showing the distribution of NT-proBNP by treatment arm and visit will be provided. NT-proBNP results will be provided in the by-subject listings as reported and values outside of the normal range will be flagged.

3.7 Immunogenicity

Anti-drug antibodies (ADA) in serum will be assessed at baseline prior to MEDI3506 administration, and at multiple time points post MEDI3506 administration during the treatment and follow-up period of the study. Blood samples for determination of ADA in serum will be assayed by bioanalytical test sites operated by, or on behalf of, AstraZeneca, using an appropriately validated bioanalytical method. Tiered analyses will be performed to include screening, confirmatory, and titer assay components. ADA results from each sample will be reported as either positive or negative. If the sample is positive, the ADA titre will be reported as well.

ADA detection at subject level:

- A subject is considered ADA positive if a collected sample is tested positive at any time during the study, including baseline and/or post-baseline.
- A subject is considered ADA negative if collected samples are tested negative at all timepoints, including baseline and post-baseline.

Treatment-related ADA development at subject level:

- Treatment-emergent ADA positive (TE-ADA positive) is defined as the sum of treatment-induced ADA positive (ADA negative at baseline and post-baseline ADA positive) and treatment-boosted ADA positive (ADA positive at baseline and boosted (≥ 4 fold) the pre-existing titre during the study period).
- Treatment-emergent ADA negative (TE-ADA negative) is defined as ADA positive but not fulfilling the definition of TE-ADA positive.

The following ADA responses variables will also be evaluated:

- Participants who are ADA positive at baseline
- Participants who are ADA positive at any post-baseline visit
- Participants who are ADA positive post-baseline and positive at baseline
- Participants who are ADA positive post-baseline and not detected (or missing) at baseline
- Participants with ADA negative post-baseline and positive at baseline
- Participants who are ADA positive at any time during the study, including baseline and/or post-baseline (also generally referred to as ADA prevalence).
- Participants who are TE-ADA positive, also known as ADA incidence.
- Participants who are ADA persistently positive, defined as ADA positive at ≥ 2 post-baseline assessments (with ≥ 16 weeks between first and last positive) or ADA positive at last post-baseline assessment.
- Participants who are ADA transiently positive, defined as negative at last post-baseline assessment and positive at only one post-baseline assessment or at ≥ 2 post-baseline assessments (with < 16 weeks between first and last positive).

For the ADA status across the study, the number and percentage of subjects with ADA responses will be summarized together with corresponding titre summaries by treatment group, according to the ADA categories defined above. For the time-course evaluation, the number of subjects with positive ADA result and ADA titres will be summarized at baseline and at all scheduled visits by treatment group. A listing of individual ADA results of all subjects will be provided.

For ADA summaries at a single time point the corresponding titre summary will be based on the titre of the positive sample for that particular visit, but for summaries across visits, the corresponding titre summaries will be based on the maximum titre of all positive samples for each subject. All valid assay results from subjects who receive any investigational product will be included in the ADA summaries. Blood samples collected at early discontinuation visit will be summarized at the closest nominal time point that does not already have a value.

To evaluate the effect of ADA on PK, descriptive statistics of MEDI3506 concentrations over time will be presented by ADA category (TE-ADA positive, ADA negative, TE-ADA negative).

Summaries of adverse events will be presented by ADA category (TE-ADA positive, ADA negative and TE-ADA negative). Summaries will include TEAEs, TEAEs by MedDRA preferred term and SOC, SAEs, and AESI. Also, the relationship between ADA category (TE-ADA positive, ADA negative and TE-ADA negative) and the percent change from baseline in EASI will be summarized.

